5.2. Participant Disposition

Participant information will be shown for all analysis sets.

The number of participants in the following disposition categories will be summarized throughout the study by vaccine regimen and overall:

- participants screened
- participants randomized
- participants in the FAS
- participants vaccinated and not randomized
- participants randomized and not vaccinated
- participants in the PPI
- participants who discontinued study
- participants who discontinued vaccination
 - reasons for termination
- participants who were unblinded during the study period

Also, the number of participants, median follow-up duration and percentage per phase will be tabulated.

5.2.1. Demographics and Baseline Characteristics

The following demographic and baseline characteristics will be summarized.

Table 6 presents a list of the demographic and baseline variables that will be summarized by vaccine regimen and overall for the FAS. This will be done for both the main study and sub study separately.

Table 6: Demographic Variables

Continuous Variables:	Summary Type
Age (years)	Descriptive statistics: N, mean, standard deviation [SD], median and range [minimum, maximum].
Weight (kg)	
Height (cm)	
Body Mass Index (BMI) (kg/m ²)	
Categorical Variables	
Sex (male, female, Intersex, Unknown)	
Age group (18-<40 years or 40-<=55 years)	
Race ^a (American Indian or Alaska Native, Asian, Black, or African American, Native Hawaiian or other Pacific Islander, White, Multiple, Not Reported)	Frequency distribution with the number and percentage of participants in each category.
ethnicity (Hispanic or Latino, not Hispanic or Latino, Not Reported, Unknown)	
Country	
BMI (underweight: <18.5 kg/m ² , normal: 18.5-<25 kg/m ² , overweight: 25-<30 kg/m ² , obese: >=30 kg/m ²)	
SARS-CoV-2 Serostatus ^b (Positive / Negative/Missing)	

^aIf multiple race categories are indicated, the Race is recorded as 'Multiple'

^bSerostatus at baseline will be based on central testing, namely S and/or non-S-based serology (e.g. N-ELISA or equivalent assay, such as the Roche Elecsys anti-SARS-CoV-2 assay), as available, and is defined as:

- Positive for participants who are positive at baseline by S-ELISA, and/or non-S-based serology (e.g. N-ELISA or equivalent assay, such as the Roche Elecsys anti-SARS-CoV-2 assay), as available.
- Negative for participants who are negative at baseline by S-ELISA, and non-S-based serology (e.g. N-ELISA or equivalent assay, such as the Roche Elecsys anti-SARS-CoV-2 assay), as available.
- Missing if data on all of the above assays are missing, or if one of the assays is missing and the other is negative.

5.2.2. Extent of Exposure

The number and percentage of participants who receive study vaccination will be summarized by vaccine group and by visit (Day 1 and Day 57). This will be done for both the main study and sub study separately.

Total Exposure:

Total exposure expressed by the total number of vaccinations received will also be summarized for the counts 1 or 2 vaccine doses by vaccine group.

5.2.3. Protocol Deviations

Major protocol deviations will be summarized. Major protocol deviations which have a potential impact on immunogenicity will be flagged in the listings.

5.2.4. Prior and Concomitant Medications

The analysis of concomitant therapies will be done using the WHO drug coded terms. Based on their start and stop date, concomitant therapies will be reported in each applicable phase.

For all participants, concomitant therapies associated with an SAE will be collected and recorded in the eCRF from the moment of first vaccination through the end of the study. Concomitant therapies associated with MAAEs will be collected and recorded in the eCRF from the moment of first vaccination until 6 months after 2nd vaccination. Concomitant therapies associated with MAAEs leading to study discontinuation will be recorded in the eCRF during the entire study. The proportion of participants with concomitant medication associated with these SAEs and MAAEs will be tabulated and listed.

For all participants, concomitant therapies such as, but not limited to, analgesic/antipyretic medications and non-steroidal anti-inflammatory drugs, corticosteroids, antihistamines, and vaccinations will be recorded from the moment of first vaccination until 28 days after administration of study vaccine, and thereafter, pre-dose on the day of any subsequent vaccination and for 28 days after that vaccination. The proportion of participants with concomitant medication will be tabulated by period.

For all participants, other concomitant therapies will also be recorded if administered in conjunction with a confirmed COVID-19 case or with new or worsening AEs reported per protocol requirements outlined in section 4.2. The proportion of participants with concomitant medication associated with these cases will be tabulated and listed.

Based on their start and stop date, concomitant therapies will be reported in each applicable phase.

If a concomitant therapy record misses components of its start and/or stop dates (time, day and/or month and/or year):

- In case of partial start or stop dates, the concomitant therapy records will be allocated to periods using the available partial information, without imputations. If, for example, only month and year are available, these will be compared to the month and the year of the periods, and the concomitant therapy record will be allocated to the period(s) where these date parts match. This rule may lead to assignment to multiple periods.
- In case of a completely missing start date, the concomitant therapy will be considered as having started before the trial.
- In case of a completely missing end date, the concomitant therapy will be considered as ongoing at the end of the trial.

The use of antipyretics with fever will be tabulated and the use of antipyretics and their impact on immunogenicity will be tabulated (overall, NSAIDs vs non-NSAIDs).

5.3. SAFETY

No formal statistical testing of safety data is planned. Safety data will be analyzed descriptively by vaccine group. In addition, for selected tables, tabulations pooled by vaccine dose will also be provided. All safety analyses will be done on the FAS. This will be done for both the main study and sub study separately.

5.3.1. Safety Endpoints

The Safety endpoints are:

Main study:

- Solicited local and systemic AEs for 7 days after each vaccination
- Unsolicited AEs for 28 days after each vaccination
- SAEs throughout the study from first vaccination until end of the study
- Adverse events of special interest (AESIs) from first vaccination until end of the study
- MAAEs until 6 months post-dose 2
- AEs leading to study discontinuation (during the entire study) for all participants following vaccination

Sub study

- Solicited local and systemic AEs for 7 days after each vaccination
- Unsolicited AEs for 28 days after each vaccination
- SAEs throughout the study from first vaccination until end of the study
- Adverse events of special interest (AESIs) from first vaccination until end of the study
- MAAEs until 6 months post-dose 2

The following section provides AE definitions associated with safety and reactogenicity endpoints.

5.3.2. Adverse Events

5.3.2.1. Definitions

Solicited AEs are used to assess the reactogenicity of the study vaccine and are predefined local (at the injection site) and systemic events for which the participant is specifically questioned, and which are noted by participants in their reactogenicity diary. Unsolicited AEs are all AEs for which the participant is not specifically questioned.

MAAEs are defined as AEs with medically attended visits including hospital, emergency room, urgent care clinic, or other visits to or from medical personnel for any reason. Routine study visits will not be considered medically attended visits. New onset of chronic diseases will be collected as part of the MAAEs. MAAEs are to be reported for all participants from the first vaccination

until 6 months after each vaccination, except for MAAEs leading to study discontinuation which are to be reported during the entire study.

Asymptomatic or undetected SARS-CoV-2 infection is defined as a participant does not fulfil the criteria of suspected COVID-19 based on sign and symptoms which would classify them as mild, moderate, or severe by the definition, and has a SARS-CoV-2 positive RT-PCR or molecular test result from any available respiratory tract sample(e.g., nasal swab sample, sputum sample, throat swab sample, saliva sample) or other sample or develops a positive serology(non-S protein) test then, the participant will be considered to have experienced asymptomatic or undetected COVID-19.

Solicited AEs shown in the tables are extracted from the investigator assessment pages (CE) of the CRF. Solicited administration site symptoms will be considered as related to the study vaccine.

For AESI, the following subcategories are defined:

- 1) Suspected AESI as reported by investigator
- 2) Suspected AESI identified through SMQ search

Those will include all reported AEs that are identified by the selection rule:

- SMQ (Standardized MedDRA Queries) = “EMBOLIC AND THROMBOTIC EVENTS (SMQ)”
or
- (SUB_SMQ1 = “HAEMATOPOIETIC THROMBOCYTOPENIA (SMQ)” and Scope in (“BROAD”, “NARROW”)) or HLT (higher level term) = “Thrombocytopenias”

- 3) Suspected AESI qualified for assessment

Suspected AESIs (reported by investigator / SMQ search) that have risk levels assessed by one of the following three criteria are considered “qualified for assessment”:

- o Brighton Collaboration Level (Level 1-5)
- o CDC Tier (non-tier 1/2, tier 1, tier 2)
- o PRAC criteria (confirmed, possible, probable, unlikely, criteria not met)

The suspected AESI will be reported from the moment of vaccination until the end of the study/early withdrawal. An AESI adjudication Committee with appropriate expertise is established to evaluate each suspected AESI and determine cases of TTS.

5.3.2.2. Severity Criteria

All AEs and laboratory data will be coded for severity using a modified version of the FDA grading table, based on the version of September 2007 (US DHHS FDA CBER 2007), included in [Appendix 2](#), Toxicity Grading Scale.

For AEs not identified in the grading table, the Severity Criteria guidelines in CTP (section 10.4.3) will be applied.

The severity of solicited signs and symptoms will be graded in the reactogenicity diary by the participant based on the severity assessment provided in the reactogenicity diary and then verified by the investigator using the toxicity grading scale in [Appendix 2](#). (Note: severity of the measured events will be derived from the diameter [for erythema and swelling] and the temperature measurements [for fever]).

5.3.3. Analysis of Adverse Events

The number and percentage of participants with at least one AE (unsolicited/solicited) will be tabulated. Unsolicited AEs will be summarized by System Organ Class and Preferred Term. Solicited AEs will be summarized by class (administration site, systemic) and preferred term.

For solicited AEs, the following tables will be provided: summary, by worst severity grade, at least grade 3, related (systemic only), time to onset (in days) and duration (in days) for most frequent events (>1%) and body temperature. Note: Duration is defined as number of days from the start of the event until resolution of the event. The time to first onset is defined as (date of first onset – reference date + 1). The reference date is the start date of the first vaccination period.

For unsolicited AEs, the following tables will be provided: summary table (including SAE, MAAEs, MAAEs leading to study discontinuation, fatal outcome, and discontinuation), all events, most frequent (>1%), at least grade 3, related and SAE. The proportion of AEs resulting in a medically attended visit (other than routine health maintenance visits) will also be tabulated.

For AESI, the following summary tables will be provided on suspected and qualified for assessment of AEs of Special Interest (AESI) by vaccine group:

1. Number of Suspected AE of Special Interest (AESI) (as Reported by Investigator) by SMQ and Preferred Term.

Note: Suspected AESI as reported by investigator and presented by: Embolic and thrombotic events (SMQ); Haematopoietic thrombocytopenias (SMQ) (broad) or HLT Thrombocytopenias; Other SMQ.

2. Number of Suspected AE of Special Interest (AESI) (Identified through SMQ search) by SMQ and Preferred Term.

Note: Suspected AESI Identified through SMQ search: Embolic and thrombotic events (SMQ), Haematopoietic thrombocytopenias (SMQ) (broad) or HLT Thrombocytopenias and presented by: Embolic and thrombotic events (SMQ) + sub-SMQ1 + PT; Haematopoietic thrombocytopenias (SMQ) (broad) or HLT Thrombocytopenias + PT;

3. Number of AESI Qualified for assessment by SMQ and Preferred Term.

Note: AESI Qualified for assessment: [Embolic and thrombotic events (SMQ)] and [Haematopoietic thrombocytopenias (SMQ) (broad) or HLT Thrombocytopenias or platelet count below normal ranges per local or central laboratory report or platelet count < 150 × 10E9/L]

Details on AESIs of thrombosis with thrombocytopenia is specified in section 8.3.6.1 of the CTP. The list of thrombotic events to be reported to the sponsor as suspected AESIs are provided Appendix 9 of the CTP. AEs meeting the suspected AESI criterion will be flagged as such in the

SDTM database. Listings and/or participant narratives will be provided as appropriate, for those participants who die, discontinue study due to an AE, or experience a serious AE or a suspected AESI.

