A target of approximately 240 participants will be enrolled in the sub study and will receive a 2-dose vaccination regimen at either 9×10^{10} vp, 5×10^{10} vp, 2.5×10^{10} vp, or 1.25×10^{10} vp. This target may not be met due to the challenges of enrolling seronegative subjects into the study, so sub-study enrollment may stop at lower numbers.

Table 2: Schematic Overview of Study Design and Groups for the Sub Study

Group	N (Seronegative)*	N (Seropositive)	Day 1 Vaccination 1	Day 57 Vaccination 2
1	~ 40	~ 20	Ad26.COV2.S 9×10^{10} vp	Ad26.COV2.S 9×10^{10} vp
3	~ 40	~ 20	Ad26.COV2.S 5×10^{10} vp	Ad26.COV2.S 5×10^{10} vp
5	~ 40	~ 20	Ad26.COV2.S 2.5×10^{10} vp	Ad26.COV2.S 2.5×10^{10} vp
6	~ 40	~ 20	Ad26.COV2.S 1.25×10^{10} vp	Ad26.COV2.S 1.25×10^{10} vp

*Due to the challenges of enrolling seronegative subjects into the study, study enrollment may stop at lower numbers.

Table 3: Humoral Immunity Blood Sampling Schedule in Participants in All Groups of the Main and Sub Study

Groups**		Month 1	Month 2	Month 3	Month 6*	
	Day 1	Day 29	Day 57	Day 71		
1 6	●	●	●	●	●	

*post last vaccination

**Groups 1, 3, 5 and 6 in the sub study

Table 4: SARS-CoV-2 Non-S Serology Schedule in Participants in All Groups of the Main and Sub Study

Groups**		Month 1	Month 2	Month 3	Month 6*	
	Day 1	Day 29	Day 57	Day 71		
1 6		●		●		

*post last vaccination

** Groups 1, 3, 5 and 6 in the sub study

Table 5: Serum Sampling and PaxGene Schedule for Innate MoA in Participants in Groups 1, 3, 5 and 6 of the Sub Study

Groups	Day 1*	Day 2	Day 4	Day 8	Day 57*	Day 58	Day 60	Day 64
1, 3, 5 and 6	●	●	●	●	●	●	●	●

*pre vaccination

MoA=mechanism of Action

An IDMC has been commissioned for the Ad26.COV2.S program. Any significant safety information will be shared with the IDMC. Refer to Committees Structure in Section 10.3, for details.

A diagram of the study design is provided in Section 1.2, Schema.

Study Duration

The study duration from screening until the last follow-up visit will be at least 8 months per participant. The study will consist of a 28-day screening phase with vaccinations on Day 1 and Day 57, and a follow-up of at least 6 months after the last vaccination.

The vaccination phase consists of the administration of 1-dose of Ad26.COV2.S on Day 1 and 1-dose of Ad26.COV2.S on Day 57. A follow-up of at least 6 months after vaccination 2, is foreseen.

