5.1.2. Phase Definitions

The phases in the study will be constructed, as follows in [Table 5](#)

Table 5: Phase Definitions

Phase	Phase #	Period	Period #	Interval	
				From	To
Screening	1			Date and time of signing the informed consent form	One minute prior to start of post dose 1 period
Post-dose	2	Post-dose 1	1	Date and time of first vaccination	Minimum of: a) 23:59 at the date of last contact (for early discontinuation) b) One minute prior to the date of unblinding visit or database cut-off date, whichever occurs first c) 23:59 on 28 days after the first vaccination (23:59 of day of vaccination + 28 days)
Follow-up 1	3			One minute after post-dose 1 period end	Minimum of: a) 23:59 at the date of last contact (for early discontinuation) b) One minute prior to the date of unblinding visit or database cut-off date, whichever occurs first c) One minute prior to date and time of second vaccination
Post-dose	2	Post-dose 2	2	Date and time of second vaccination	Minimum of: a) 23:59 at the date of last contact (for early discontinuation) b) One minute prior to the date of unblinding visit or database cut-off date, whichever occurs first c) 23:59 28 days after the second vaccination (23:59 of day of vaccination + 28 days)
Follow-up 2	4			One minute after post-dose 2 period end	Minimum of: a) 23:59 at the date of last contact (for early discontinuation) b) One minute prior to the date of unblinding visit or database cut-off date whichever occurs first

					c) One minute prior to 6 months after second vaccination
Follow-up 3	5			One minute after post-dose 2 period end	
Minimum of:
 
a) 23:59 at the date of last contact (for early discontinuation)
 
b) One minute prior to the date of unblinding visit or database cut-off date, whichever occurs first
 
c) 23:59 at the date of last visit

Note: the end of regimen phase should be the end of the last post dose period

FU3: Full follow-up from end of post dose 2 to end of study or last contact

Post-dose 1 and post dose 2 Combined includes events occurring in the post-dose 1 and/or post dose 2 phases (not including FU 1 or FU2 or FU3)

For final analysis the following criteria for Follow-Up 3 will be used 23:59 at date of last contact (for early discontinuation or date of last visit)

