5.1.3. Visit Windows

Per-protocol visit windows (refer to CTP section 1.4) guide study procedures. Analysis visit windows are defined considering the emerging data from other studies relating to sampling time points and potential impact on immunogenicity. As such, analysis windows may be redefined prior to unblinding. No time windows apply for Early Exit visit sampling.

The following visit window rules will be considered for the analysis of immunogenicity results:

For vaccination:

1. If a participant missed a scheduled vaccination, all immunogenicity samples taken after the missed vaccination will be excluded from the PPI. Samples taken before will still be included in the PPI.
2. If the scheduled vaccination at vaccination visit Day 57 is $\geq -9/+16$ days from planned vaccination date (outside Day 49- Day 72), all immunogenicity samples taken after will be excluded from the PPI. I.e., if the vaccine is administered at least 9 days before or at least 16 days after the planned vaccination date, all immunogenicity samples taken on or after will be excluded from the PPI set.

For immunogenicity sampling (excluding D2, D4, D8, D58, D60 and D64 for sub-study participants):

1. If immunogenicity sample is taken out of window when planned within three months (≤ 3 months) post dose 1 vaccination (i.e. up to and including Day 71 visit), the sample will be excluded from PPI as follows:
 - a. For sampling at D29 if taken $\geq -/+9$ days from the planned Visit date.
 - b. For sampling at D57 if taken $\geq -9/+16$ days from the planned Visit date.
 - c. For sampling at D71 if taken $\geq -4/+16$ days from the planned Visit date.

For example, samples outside the following windows will be excluded:

- a) Post Vac 1 + 28-day visit (D29): samples taken outside 21 days and up to 37 days post vaccination 1 will be excluded.

b) Vac 2 visit (D57): samples taken outside 49 days and up to 72 days post vaccination 1 will be excluded.

c) Post Vac 2 + 14 day visit (D71): samples taken outside 11 days and up to 29 days post vaccination 2 will be excluded.

d) Other samples from these participants can still be included in PPI.

2. If immunogenicity sample is taken out of window when planned 24 weeks post last vaccination and thereafter, this sample will be excluded from PPI if taken $\geq/-/+ 30$ days from Visit timing date. Other samples from this participant can still be included in PPI.

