5.3.3.1. Phase Allocation of Adverse Events

Solicited events are always allocated to the respective Post Dose period.

Step 1: Allocation of events to the periods:

Adverse events in the SDTM data base are allocated to periods based on their start date/time. If the start date/time of an event falls between (or on) the start and stop date/time of a period, the AE is attributed to that period (treatment-emergent principle).

- In case of partial start or stop dates (i.e. time and/or day and/or month and/or year missing), the events are allocated to the periods using the available partial information on start and end date; no imputation will be done. If, for instance, the AE start date only month and year are available, these data are compared to the month and year information of the periods. This rule may lead to multiplication of the event as a consequence of its assignment to multiple periods.
- In case of a completely missing end date, the date is imputed by the cut-off date of the analysis for participants still ongoing in the study, and by the end date of the last period for participants who discontinued or completed the trial. In case of a completely missing start date, the event is allocated to the first active treatment phase (post dose 1 period), except if the end date of the AE falls before the start of the first active treatment phase (post dose 1 period).

Step 2: Combination of events:

Overlapping/consecutive events are defined as events of the same participant with the same preferred term which have at least 1 day overlap or for which the start date of an event is 1 day after the end date of the preceding event. Overlapping/consecutive events may be combined into one AE or not, according to the following rules:

1. If overlapping/consecutive events start in one of the following periods - Screening or post dose extension (i.e. non-active periods) - followed by an AE in - post-dose period (active period) - they are allocated to their respective periods and are considered as separate events.
2. In case overlapping/consecutive events start within a single period, they are considered as one and the same AE. The individual events which contribute to this AE are retained as individual records in the ADaM data base but are assigned the same onset, period, and total duration. All related attributes to the AE/phase/period should also be consistent with the new event.

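### The onset rule for solicited adverse events names only the first vaccination as reference date, so post-dose 2 onsets, if programmed literally, would fall around day 57–64 instead of day 1–8

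*SAP*

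**What the plan says.** SAP 5.3.3 lists time to onset, in days, among the tables for solicited adverse events, for events above a 1% frequency. It gives the formula, "The time to first onset is defined as (date of first onset – reference date + 1", and fixes one term of it: "The reference date is the start date of the first vaccination period". Nothing in the section supplies a reference date for the second dose.

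Four other places bear on this:

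- SAP 5.3.1 defines the endpoint per dose: "Solicited local and systemic AEs for 7 days after each vaccination".
- SAP 5.3.3.1 assigns each event to its own dose: "Solicited events are always allocated to the respective Post Dose period".
- SAP 5.1.2, Table 5, starts the post-dose 1 period at "Date and time of first vaccination". It ends Follow-up 1 one minute before the "date and time of second vaccination", which is where the post-dose 2 period begins.
- SAP 5.1.1 defines relative day by the same formula, but lets the reference date be that of vaccination 1 or of vaccination 2. That rule is written for visits and analysis time points, not for adverse event onset.

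**The concern.** Time to onset of a reaction is useful as the delay since the injection that provoked it. The rule gives that delay for dose 1. For dose 2 it gives the delay plus the interval between doses. A reaction filed under post-dose 2 would then carry an onset day counted from a different injection.

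Two things would be lost in that table. Onset after dose 1 and onset after dose 2 could not be read side by side without correction. The spread of the dose-2 values would also partly reflect when participants attended for vaccination 2, not how quickly they reacted. Safety and reactogenicity by dose level is a secondary objective, and this is one of the tables that describes it.

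**Working it through.** **Inputs**

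- Onset formula and reference date: SAP 5.3.3. The phrase used for the reference period is not a label in Table 5. Its natural reading is the post-dose 1 period, which starts on Day 1.
- Schedule: "vaccinations on Day 1 and Day 57" (Protocol 4.1).
- Window for vaccination 2: −3/+7 days (Protocol 1.4.1 and 1.4.2), so Day 54 to Day 64.
- Solicited collection: the vaccination day and the seven days after it (Protocol 8.3.2), so k = 0 to 7 days after the injection.
- Wider range, for sensitivity only: the SAP 5.1.3 rule that drops immunogenicity samples when vaccination 2 is "outside Day 49- Day 72". That rule governs the per-protocol immunogenicity set. It does not restrict the safety tables.

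**Check of the day count.** With Day 1 as the first vaccination and vaccination 2 on Day 57, the contacts 7, 14 and 28 days later fall on 57 + 7 = 64, 57 + 14 = 71 and 57 + 28 = 85. These are the Day 64, Day 71 and Day 85 of the schedule of activities, so the convention is reproduced. The documents state no onset-day range to compare with.

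**Formulas.** Let V be the study day of vaccination 2.

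- Literal rule: (V + k) − 1 + 1 = V + k.
- Reference at vaccination 2: (V + k) − V + 1 = k + 1.
- Difference: (V + k) − (k + 1) = V − 1, which does not depend on k.

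**Results for events after dose 2**

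| Day of vaccination 2 | Onset, literal rule | Onset, own-dose reference | Added days |
|---|---|---|---|
| 57 (nominal) | 57–64 | 1–8 | 56 |
| 54–64 (protocol window) | 54–71 | 1–8 | 53–63 |
| 49–72 (sensitivity) | 49–79 | 1–8 | 48–71 |

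For example, a reaction starting on Day 58 after a Day 57 injection gives 58 − 1 + 1 = 58 under the literal rule, and 58 − 57 + 1 = 2 from its own dose. Within the protocol window, visit timing alone adds up to 63 − 53 = 10 days of spread.

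Dose-1 events give 1 + 0 − 1 + 1 = 1 up to 1 + 7 − 1 + 1 = 8 under either rule.

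**Pooled tables.** The derivation uses the date of first onset. A participant who had the event after dose 1 therefore contributes that dose-1 onset, correctly counted, to a table pooled over doses. Only a participant whose first occurrence follows dose 2 contributes a displaced value.

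**The case against.** The best defence is that the surrounding text already points to per-dose handling. SAP 5.1.1 presents safety results by phase and uses vaccination 1 or 2 as the reference for relative days. SAP 5.3.3.1 keeps each solicited event with its own dose. On this view the sentence in 5.3.3 is a drafting slip that a programmer would see through. The programming instructions also sit in a separate Data Presentation Specifications document, so the actual outputs cannot be judged from the SAP. It probably is a slip, but the defence does not cure it. The relative-day rule covers visits and time points, while the onset rule is specific and explicit. The SAP introduction says that the SAP specifies key derived variables, so correct programming would depart from the plan as written.

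It is also fair to say that little rests on the table. Safety is descriptive, with no formal testing (SAP 5.3). Protocol 9.4.3 plans solicited events by frequency, severity and duration and does not list time to onset. Injection dates are recorded in the eCRF (Protocol 6.4), so correct values can always be derived, and a post-dose 2 table centred near day 57 would be noticed at review. All of this stands, and it limits the weight of the point.

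A reader might infer more than the documents support:

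- *That every solicited onset is miscounted.* It is not: dose-1 onsets are right, and so is any pooled value from a participant who had the event after dose 1.
- *That a pooled mean would be about a month.* This would need roughly half of the contributing participants to have their first occurrence after dose 2. No document gives that share, and a share of events would not translate into a share of first onsets.
- *That day 54–71 bounds all dose-2 values.* It holds only inside the protocol window. Protocol 6.1 and Section 8 allow vaccination outside it in some circumstances, and the full analysis set used for safety has no window exclusion.

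**Conclusion.** The rule is wrong as written for the second dose, and no other section overrides it. Taken literally, it displaces each post-dose 2 onset by the participant's own dose interval: 56 days on the nominal schedule, 53 to 63 days inside the protocol window, and more or less than that for out-of-window vaccinations. This rests on reading the reference period as post-dose 1 and on the sentence being programmed literally. The documents do not show whether it was.

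The consequence is narrow. Post-dose 2 time-to-onset tables are affected throughout. Pooled tables are affected only for participants whose first occurrence follows dose 2. Incidence, severity, duration, period allocation and the primary non-inferiority analysis are untouched. It is a small correction, worth making because the table would otherwise mislead and because the SAP disagrees with its own per-dose convention.

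**What to change.** Replace the reference-date sentence in SAP 5.3.3 with:

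> The reference date is the start date of the post-dose period to which the event is allocated (date of vaccination 1 for post-dose 1, date of vaccination 2 for post-dose 2).

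This agrees with SAP 5.1.1, Table 5 and SAP 5.3.3.1. Dose-2 onsets then run from day 1 to day 8 whatever the date of vaccination 2, and dose-1 results do not change. The Data Presentation Specifications should be checked for the same wording. The cost is one sentence. No new data are needed, and no other analysis changes.
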